- a. Physical risks to the subjects Yes No
- b. Social Risks Yes No
- c. Psychological risks to subjects Yes No
- d. Discomfort to subjects Yes No
- e. Invasion of the body Yes No
- f. Invasion of privacy Yes No
- g. Disclosure of information damaging to subject or others Yes No

3. Does the study involve?

- a. Use of records (Hospital, medical, Death, birth or other) Yes No
- b. Use of foetal tissue or abortus Yes No
- c. Use of organs or body fluids Yes No

4. Are subjects clearly informed about?

- a. Nature and purposes of study Yes No

- b. Procedures to be followed including alternatives used N/A
- c. Physical risks N/A
- d. Private questions Yes No
- e. Invasion of the body N/A
- f. Benefits to be derived Yes No
- g. Right to refuse to participate or to withdraw from study Yes No
- h. Confidential handling of data Yes No
- i. Compensation where there are risks or loss of working time or privacy is involved in any particular procedure Yes No

5. Will signed consent form/verbal consent be required?

- a. From subjects Yes No
- b. From parent or guardian (if subjects are minors) Yes No

6. Will precautions be taken to protect anonymity of subject? Yes No

RESEARCH PROTOCOL

- **Project Title:** A Study on Artificial Intelligence Algorithms for Breast Cancer Classification from Histopathology Images
- **Summary:** Breast cancer, a widespread and potentially fatal illness, emphasizes the urgent requirement for early and precise detection to enhance patient outcomes. The current diagnostic framework, characterized by manual histopathological examination, exhibits inherent drawbacks such as subjectivity and limited throughput. In response, our research aims to transform breast cancer diagnostics by leveraging advanced computational techniques, particularly deep learning. Breast cancer can be classified into two main subtypes: invasive and noninvasive.

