Noninvasive breast cancer, often termed *in situ* breast cancer, is characterized by abnormal cells confined within the milk ducts (ductal carcinoma *in situ* or DCIS) or lobules (lobular carcinoma *in situ* or LCIS) without invading surrounding tissues. This type is considered an early stage and typically not life-threatening on its own. Invasive breast cancers are those that spread from the original site (either the milk ducts or the lobules) into the surrounding breast tissue. These constitute approximately 70% of all breast cancer cases and generally have a poorer prognosis compared to the *in-situ* subtypes. [1]

Medical imaging of breasts can be acquired through various techniques, such as MRI scans, mammography, ultrasound, thermography, computed tomography scans, and histopathology. Among these approaches, the histopathology test serves as the gold standard for the clinical diagnosis of cancer. [2]

The proposed AI model aims to streamline and enhance the analysis of histopathological images for the classification of invasive and noninvasive breast cancer, surpassing conventional methods and providing a reliable means of identifying cancerous regions. This promises to significantly improve the accuracy and efficiency of breast cancer diagnostics, meeting the urgent need for dependable and scalable solutions. By automating the complex process of breast cancer histopathological image analysis, our goal is to democratize screening, making it more accessible and reaching underserved populations. Moreover, our model goes beyond technological innovation; it addresses broader issues of accessibility and scalability, particularly in low-income settings. The research's focus on domain adaptation is crucial, ensuring the model's accuracy and reliability across various health facilities. This involves accommodating differences in resources, equipment, and demographic factors, making it a versatile and adaptable solution for diverse contexts.

In summary, our research not only aims to advance the technological frontier in breast cancer diagnostics but also seeks to drive a transformative change in accessibility,

efficiency, and reliability. By developing an AI model that tackles the specific challenges of traditional methods, we aim to make a meaningful impact on breast cancer screening, ultimately leading to early detection, tailored treatment, and improved outcomes for patients worldwide.

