Manual examination of histopathological images is labor-intensive and taxing. Moreover, there's a significant risk of overlooking small cancerous regions on slides, especially as malignant cells may be sparsely distributed. In this scenario, machine learning-based automated inspection techniques offer rapid and dependable identification of invasive and noninvasive cancerous cells and regions on the slide. [5] Diagnoses heavily depend on the expertise of medical professionals, introducing subjectivity and limited repeatability, with documented inaccuracies even among experienced practitioners.

Traditional vision screening of histopathological images via light microscopy poses risks of misdiagnosis and struggles with accessibility due to time and personnel limitations. The primary focus is on leveraging advanced computational techniques to automate analysis, addressing inherent drawbacks in traditional screening methods. Through AI approaches, our aim is to create a model surpassing the accuracy of visual assessments, providing a reliable and efficient means of identifying transformation zones and detecting early signs of breast abnormalities. Central to our objective is the recognition of the need for scalable and cost-effective solutions, particularly in low-income settings. The proposed AI model seeks to mitigate the shortage of trained personnel by automating breast cancer histopathological image analysis, streamlining screening and enhancing accessibility. Moreover, we aim to incorporate domain adaptation techniques to ensure the model's precision and resilience across diverse health facilities, considering challenges such as resource constraints, equipment variations, and demographic diversity.

- **Objectives:** Our primary goal is to compile a diverse dataset of breast tissue histopathology images, incorporating samples from various sources to ensure representation across patient demographics and imaging equipment. Using this dataset, we aim to develop a robust AI model for automated classification of invasive and noninvasive breast cancer within histopathology images. Specific objectives include:
 - a) Clinical Validation: Evaluate the AI model's performance through comprehensive clinical validation, measuring sensitivity, specificity, and accuracy in classifying invasive and noninvasive breast cancer types in histopathology images.

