 - b) Usability Assessment: Assess the model's usability by involving healthcare professionals in the evaluation process, measuring integration into clinical workflows, result interpretability, and time efficiency during histopathology examinations.
 - c) Impact on Early Detection: Investigate the AI model's impact on early breast cancer detection, analyzing its contribution to identifying cancer types at earlier stages for potentially improved patient outcomes.
 - d) Generalizability: Evaluate the model's generalizability across diverse datasets, including local sources, assessing its performance in different regions and healthcare settings for broader clinical applicability.
 - e) Impact on Patient Outcomes: Examine the AI model's impact on patient outcomes, such as reduced diagnosis time, increased accuracy in cancer type identification, and enhanced treatment planning, considering potential benefits to patient well-being and satisfaction.
 - f) Clinical Decision Support: Evaluate the model's effectiveness as a clinical decision support tool, measuring its contribution to accurate diagnoses and treatment plans during histopathology examinations.

Through these objectives, our research aims to advance breast cancer diagnosis, providing a comprehensive solution that integrates seamlessly with clinical practices and positively influences patient outcomes.

- **Rationale:** Histopathology images contain valuable information about tissue structure, but manual interpretation can be subjective and time-intensive. Deep learning offers a promising solution by automatically learning complex patterns, potentially improving the accuracy and efficiency of breast cancer classification. This research aims to leverage deep neural networks to analyze extensive datasets of histopathology images, distinguishing between invasive and noninvasive breast cancer with high accuracy. Automating this classification process aims to reduce human error, expedite diagnoses, and support personalized treatment approaches. Ultimately, the goal is to refine breast cancer diagnosis, enabling earlier intervention and better patient outcomes.

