b) **Sample size calculation:** Following the methodology of sample size calculation to evaluate diagnostic performance (for algorithms in this case), we use the following method of calculation for a target sensitivity and specificity incorporating disease prevalence [7]:

$$N_{sen} \geq \frac{Z^2(1-\alpha)/2 \times sen(1 - sen)}{c^2 \times p}$$

$$N_{spec} \geq \frac{Z^2(1-\alpha)/2 \times spec(1 - spec)}{c^2 \times (1 - p)}$$

N_{sen} = Required sample size for sensitivity, sen
 N_{spec} = Required sample size for specificity, $spec$
 α = Confidence level
 $Z^2(1-\alpha)/2$ = The Z-score for the confidence level α
 p = Prevalence of breast cancer
 c = Confidence interval
 sen = Estimated sensitivity
 $spec$ = Estimated specificity

- The final sample size N is calculated based on the larger of the two values N_{sen} and N_{spec} . In this study, as we are using deep learning techniques, we need the medical image samples to reflect the various cancerous, precancerous and normal cases. For our analysis, we assume an 80% confidence level ($\alpha = 0.80$) and prevalence of breast cancer for self-reported instances, $p = 0.261$ [23]. A confidence interval of 5% is selected ($c = 0.05$). We estimate the sensitivity and specificity of our algorithms to be at 75% ($sen = 0.75$ and $spec = 0.75$). Using these values, we obtain the sample size values: $N_{sen} = 471$ and $N_{spec} = 166$. Since $N_{sen} > N_{spec}$, the final sample size for the study will be:

$$N = N_{sen} = 471$$

We can set a target of $N = 500$.

c) Procedures: During the prospective phase of the study, data collection will occur in clinical settings. Eligible patients will be approached during clinic visits and presented with a consent form for their review. Upon agreement, each participant will be assigned a unique identifier to maintain data integrity and ensure patient anonymity. Subsequently, patients will provide essential clinical information. Healthcare professionals will conduct histopathological examinations, and specialized equipment available in the clinic will be used to capture images of the breast region. This method guarantees the collection of non-identifiable data, unique data identifiers, and informed consent directly within the clinical setting, meeting the specific requirements of histopathological breast cancer screening.

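### N = 500 is sized for cancer versus no cancer, but objective (a) measures sensitivity and specificity for invasive versus noninvasive cancer; ±5 points is not shown for that target and no class counts are fixed

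*Protocol*

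**What the plan says.** **What is sized.** Protocol, Methodology b) Sample size calculation, divides by p for sensitivity and by 1 − p for specificity, with p defined as the prevalence of breast cancer. The inputs are 80% confidence and "prevalence of breast cancer for self-reported instances, $p = 0.261$ [23]. A confidence interval of 5% is selected" (c = 0.05). On performance it says "We estimate the sensitivity and specificity of our algorithms to be at 75" per cent. The results are 471 for sensitivity and 166 for specificity; the larger is taken and the target is set at 500.

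**What the objectives measure.** The Summary says "Breast cancer can be classified into two main subtypes: invasive and noninvasive" and equates noninvasive with in situ disease, ductal or lobular. It describes the model as being "for the classification of invasive and noninvasive breast cancer, surpassing conventional methods". Under Objectives, "we aim to develop a robust AI model for automated classification of invasive and noninvasive breast cancer within histopathology images". Objective (a), Clinical Validation, is the only one of (a) to (f) that names sensitivity and specificity, and it does so for "measuring sensitivity, specificity, and accuracy in classifying invasive and noninvasive breast cancer types in histopathology images". The Rationale repeats the purpose: "distinguishing between invasive and noninvasive breast cancer with high accuracy".

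**What other sections say.** Methodology a) Study Population gives the primary aim as telling patient groups apart: confirmed cancers, lesions that resemble cancer, and suspected or normal cases. It also admits women of unknown test status, for unsupervised learning. Methodology e) Data Interpretation has the model predict whether an abnormality is present, and promises a balanced dataset without naming classes or counts. Methodology f) Statistical Analysis attaches sensitivity and specificity to classifying and detecting abnormalities.

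**The concern.** In the formulas every cancer is a positive and every other patient a negative. For objective (a) the positives and the negatives are both cancers, and patients without cancer add nothing to either proportion. The cancers that just suffice for the sensitivity of detection would have to be divided between two classes, each of which needs about that many on its own.

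A reader who goes from the Objectives to the sample size section will take 75% ±5 points as the precision of the clinical validation. The section ties its 75% to the algorithms in general and does not limit it to one target. No invasive share and no number per subtype enters the calculation, so the precision of objective (a) is nowhere shown.

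**Working it through.** **Inputs** (Protocol, Sample size calculation): sen = spec = 0.75, so sen × (1 − sen) = 0.1875; c = 0.05; p = 0.261; 80% confidence, two-sided z = 1.28 (1.2816 to four places); N = 500. Each patient is taken as evaluated once, and all 500 as evaluated.

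**1. The plan's own figures.** With z = 1.28:
- N_sen = 1.6384 × 0.1875 / (0.0025 × 0.261) = 470.8 (stated 471)
- N_spec = 1.6384 × 0.1875 / (0.0025 × 0.739) = 166.3 (stated 166)

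Both reproduce, so c acts as a half-width and the arithmetic is sound.

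**2. Patients needed per class for ±5.** n = z² × 0.1875 / 0.0025 = 122.9 with z = 1.28, or 123.2 with z = 1.2816. That is 123 to 124 in each class, the same number that 471 × 0.261 = 122.9 cancers supplies.

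**3. Cancer versus no cancer at N = 500.** If 26.1% are cancers, there are 130.5 cancers and 369.5 others. Half-width = 1.2816 × √(0.1875/n):
- sensitivity, n = 130.5: ±4.9 points
- specificity, n = 369.5: ±2.9 points

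The sizing delivers its ±5 for this target, provided the sample has that mix.

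**4. Objective (a) at the same mix.** Two classes at ±5 need 246 to 248 cancers (248/500 = 49.6%), against about 130.

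| Split of 130.5 cancers | Smaller class | Half-width, smaller class |
|---|---|---|
| 50/50 | 65.25 | ±6.9 |
| 70/30 | 39.15 | ±8.9 |
| 80/20 | 26.1 | ±10.9 |

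An even split is the best case, with ±6.9 in each class. The 70/30 row only illustrates the Summary's background statement on invasive cancers, "These constitute approximately 70% of all breast cancer cases"; its larger class (91.35) has ±5.8. The protocol does not plan that share for this sample.

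**5. An enriched mix.** Equal thirds of 500 (invasive, noninvasive, no cancer) give 166.7 per class: 1.2816 × √(0.1875/166.7) = 0.043, or ±4.3. Here ±5 is met with no change in N.

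**The case against.** **Detection is the real target, and the sizing fits it.** This has force. Study Population labels the separation of patient categories as the primary aim, and Statistical Analysis attaches the metrics to abnormalities. Objective (a) is one of six, and a plan need not size every objective. What stands against this is that the Summary, Objectives and Rationale all make the subtype split the purpose of the model. Abnormality is not the same class as cancer either. The protocol should say which target is primary and which one was sized.

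**A case-control, balanced sample need not contain 26.1% cancers.** This is correct, and it bars the stronger reading that objective (a) will miss ±5 or that 500 is too few. Step 5 shows a mix that meets it. But balance is promised without classes or counts, so it does not show adequacy. The same argument applies to cancer versus no cancer: the ±4.9 and ±2.9 also depend on a mix that the design does not guarantee.

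**Noninvasive might mean everyone without invasive cancer.** The Summary's definition as in situ cancer says otherwise. Under the broader reading, with the illustrative 70% share, the negatives would number 408.65 (±2.7), while invasive cases would stay at about 91 (±5.8).

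**Women of unknown status are not meant for evaluation.** This is largely fair: they are included for unsupervised learning, test results are the ground truth, and the inclusion criteria ask for biopsy availability and confirmatory records. What stays open is whether they count toward the 500, where the margin over 471 is 29.

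**Conclusion.** The inconsistency is real. The stated size and precision belong to cancer versus no cancer, while the only objective that names sensitivity and specificity concerns a split within the cancers. At the protocol's own p = 0.261 and N = 500, ±5 cannot hold for both subtypes at any split: about 130 cancers against 246 to 248 needed, with ±6.9 each at best. This assumes 75% in each class, 80% confidence, one result per patient, all 500 evaluated, and noninvasive meaning in situ cancer.

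A reader might go further and infer that the calculation is wrong, that the trial is too small, or that ±5.8 and ±8.9 are the expected precisions. The document supports none of these. The arithmetic reproduces, an enriched mix can meet ±5 within 500, and the 70/30 figures combine a prevalence with a background share that the protocol does not plan to sample. The precision for objective (a) is undetermined rather than shown to be inadequate.

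**What to change.** 1. Reconcile Objectives, Study Population, Data Interpretation and Statistical Analysis. Name one primary classification target, with its positive and negative classes.
2. In the sample size section, state that the calculation is for cancer versus no cancer. Add that its ±5 requires at least about 123 to 124 confirmed patients in each class, which means roughly 26% or more cancers among those evaluated (26.1% of 471; 124/500 = 24.8% if all 500 are evaluated).
3. For objective (a), choose one of three: plan at least about 124 confirmed invasive and 124 confirmed noninvasive patients within the 500; restate its precision from whatever counts are planned; or say that its precision depends on case mix and that ±5 is not claimed. The 70/30 figures above are not text to insert.
4. Count only patients with a confirmed reference result toward any stated precision.

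No increase in N is required. The cost is wording in these sections, plus either a commitment on case mix or a wider or conditional precision for objective (a).

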In the retrospective phase of the study, additional data will be retrieved from the clinic's database of prior screenings. Due to the retrospective nature, obtaining consent from individual patients is impractical. To address privacy concerns, any personally identifiable patient information will be systematically excluded from the collected data. This ensures compliance with privacy standards while leveraging valuable information from past screenings. While informed consent cannot be obtained for this dataset, the study will strictly adhere to ethical guidelines and prioritize patient privacy during the data extraction process from the clinic's database.

d) Methods of Data Collection:

- Patient ID (unique identification number)
- Date & Time of data input
- Age
- Histopathological breast image data
- Region of Interest (ROI) Annotations:
 - Lesion size
 - Provisional diagnosis
 - Suggested management (e.g., routine screening, biopsy, etc.)
 - Patient's relevant medical/surgical history
- Additional Information (if available):
 - Relevant diagnostic test results
 - Reproductive history

The hematoxylin and eosin (H&E) stained images obtained from histopathological assessment, along with relevant metadata, will significantly contribute to algorithm design and image analysis. These

images' standard test status and corresponding results will serve as the ground truth for our detection algorithm.

e) **Data Interpretation:** Following the completion of data collection, exploratory data analysis will be conducted to assess patient distribution across various parameters, including transformation zone type, histopathology, and relevant clinical factors. Subsequently, a balanced dataset will be curated to ensure fair representation of image samples.

This curated dataset will serve as the foundation for training and evaluating the artificial intelligence (AI) algorithm developed for automatic classification and detection of abnormalities in histopathological breast screening cases. The trained model will generate predictions regarding the presence or absence of abnormalities in the breast images.

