To validate the accuracy and clinical relevance of the algorithm's predictions, the results will undergo verification and analysis in collaboration with expert histopathologists. Their insights will be invaluable in refining the automatic algorithm, thereby improving its precision in classifying and detecting potential abnormalities during histopathological breast screenings.

f) **Statistical Analysis:** Once the dataset becomes available, statistical analysis will center on evaluating the performance of the developed artificial intelligence algorithms for automatic classification and detection of abnormalities in histopathological breast screening cases. Key metrics such as sensitivity, specificity, precision, recall, F-1 score, and overall accuracy will be utilized for rigorous evaluation. To ensure robustness, experiments involving n-fold cross-validation will be performed, with mean values and standard deviations of performance metrics calculated. This analysis will conclude with a comparative assessment of various deep learning models, assessing their effectiveness in the automatic classification task.

Utilization of Results: The study results will be pivotal in the development and assessment of an automatic detection algorithm for breast cancer screening, with the following primary objectives:

- a) **Automatic Detection:** Evaluate and detect potential abnormalities in histopathological images, furnishing an automated screening tool for efficient identification of breast cancer risk.
- b) **Clinical Decision Support:** Aid healthcare professionals by furnishing an automated analysis to assist in prioritizing treatment strategies and making informed clinical decisions based on the algorithm's findings.

c) Systematic Data Storage: Enable systematic storage of histopathological images and pertinent metadata to bolster ongoing research efforts, all while safeguarding individuals' privacy during the automated detection process.

These outcomes are poised to significantly enhance the efficiency and accuracy of breast cancer screening, offering valuable support to healthcare professionals in Bangladesh.

- **Facilities:** In the case of collecting data from histopathological breast cancer screening, no additional facilities are required except those the clinics are already equipped with (e.g. image acquisition and data storage capacity).

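### The model is to be evaluated on a dataset balanced after collection, so its precision, F1 and accuracy describe a constructed case mix and not the clinic's

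*Protocol*

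**What the plan says.** Methodology e) Data Interpretation sets the order of work. After collection and exploratory analysis, "Subsequently, a balanced dataset will be curated to ensure fair representation of image samples". The next sentence gives that set both roles: "This curated dataset will serve as the foundation for training and evaluating the artificial intelligence (AI) algorithm".

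Methodology f) Statistical Analysis then lists the measures: "Key metrics such as sensitivity, specificity, precision, recall, F-1 score, and overall accuracy will be utilized for rigorous evaluation". They are to be estimated by n-fold cross-validation, and "This analysis will conclude with a comparative assessment of various deep learning models".

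Utilization of Results describes the product as "furnishing an automated screening tool for efficient identification of breast cancer risk", and also as decision support for treatment priorities.

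The protocol does not state which variable is balanced, at what ratio or by what method. It sets aside no evaluation data at the collected or clinical mix, and it plans no reweighting to a prevalence.

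**The concern.** Equalising classes can help a network learn. It has no such purpose in the data used to measure the network's performance. Folds drawn from a balanced set are themselves balanced, so cross-validation does not restore the lost mix.

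In a screening or decision aid, precision tells the clinician how far to trust a positive result. If precision and F1 come from a constructed mix, they do not answer that question for the clinic population. The model comparison is exposed too: F1 and accuracy can rank two models one way at a balanced mix and another way at the clinic's mix, so the less suitable model could be preferred.

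**Working it through.** **Inputs from the protocol.** Sensitivity (se) 0.75, specificity (sp) 0.75, prevalence p = 0.261, half-width c = 0.05 and 80% confidence, all from Methodology b) Sample size calculation. The Summary says of invasive cancers: "These constitute approximately 70% of all breast cancer cases".

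**Assumptions.** The meaning of balanced (1:1, or equal thirds), a target prevalence range of 20% to 40%, and the two illustrative models below.

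**The plan's own figure.** With z = 1.28:

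- N_sen = 1.28² × 0.75 × 0.25 / (0.05² × 0.261) = 470.8 (stated: 471)
- N_spec = 1.28² × 0.75 × 0.25 / (0.05² × 0.739) = 166.3 (stated: 166)

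These reproduce to rounding. The sample size is not affected by this point. The check only confirms that se, sp and p are used here as the plan uses them.

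**Formulas.**

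- Precision = se·p / [se·p + (1 − sp)(1 − p)]
- F1 = 2 × precision × se / (precision + se)
- Accuracy = se·p + sp·(1 − p)

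**Worked example, se = sp = 0.75.** At p = 0.50, precision = 0.375 / (0.375 + 0.125) = 0.750. At p = 0.261, precision = 0.19575 / (0.19575 + 0.18475) = 0.514, and F1 = 2 × 0.514 × 0.75 / (0.514 + 0.75) = 0.610.

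| Positive fraction p | Reading | Precision | F1 | Accuracy |
|---|---|---|---|---|
| 0.20 | assumed lower target | 0.429 | 0.545 | 0.75 |
| 0.261 | protocol's prevalence | 0.514 | 0.610 | 0.75 |
| 1/3 | cancerous, precancerous, normal in equal thirds | 0.600 | 0.667 | 0.75 |
| 0.40 | assumed upper target | 0.667 | 0.706 | 0.75 |
| 0.50 | balanced 1:1 | 0.750 | 0.750 | 0.75 |
| 0.70 | invasive share of breast cancers | 0.875 | 0.808 | 0.75 |

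For cancer detection, a 1:1 set overstates precision and F1 relative to 0.261. For invasive versus noninvasive, with invasive as the positive class and about 70% of cancers invasive, it understates them: 0.75 against 0.875 for precision and 0.75 against 0.81 for F1. Accuracy stays at 0.75 in every row only because se equals sp.

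**Model ranking (illustrative).** Model A has se 0.90 and sp 0.70. Model B has se 0.70 and sp 0.90.

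| p | A: F1 | B: F1 | A: accuracy | B: accuracy |
|---|---|---|---|---|
| 0.50 | 0.818 | 0.778 | 0.800 | 0.800 |
| 0.261 | 0.655 | 0.706 | 0.752 | 0.848 |

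For example, accuracy of A at 0.261 = 0.90 × 0.261 + 0.70 × 0.739 = 0.752. At 1:1, A leads on F1 and the two tie on accuracy. At 0.261, B leads on both.

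**The case against.** The strongest reply has four parts.

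- **Balanced need not mean class balance.** The protocol also wants representation across demographics and equipment, and balancing on those might barely move the cancer fraction. The variable is indeed undefined, so the figures are conditional. But histopathology is among the factors explored immediately before balancing, and the sample size section says "we need the medical image samples to reflect the various cancerous, precancerous and normal cases". Class balance is the natural reading.
- **The design is case-control, so the collected mix is already artificial.** True, and un-resampled test folds alone would not give clinic precision. That is a reason to reweight. It does not justify a second artificial mix. Nor is this merely a detail left to an SAP: the protocol commits positively to evaluating on the curated set.
- **The study is sized on sensitivity and specificity, and accuracy does not move at 75%/75%.** Both statements are correct, and they limit the harm. Precision and F1 are still named key metrics, and accuracy moves once se and sp differ.
- **The numbers are fragile.** The value 0.261 is labelled as self-reported prevalence and cited to reference 23, while the reference list ends at 7. It is not shown to be the prevalence among biopsied clinic patients. The 70% refers to all breast cancers, no comparison metric is named, and models A and B are invented. They show that a reversal is possible, not that it will occur.

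One further caveat stands. Reweighting to a single prevalence corrects the class ratio only. If the blend of benign mimics and normal tissue differs from the clinic's, specificity, and so reweighted precision, can still be off.

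**Conclusion.** The concern holds. Followed as written, the plan reports precision, F1 and, in general, accuracy at a case mix created by curation, with no step that carries them back to the clinic. Under a 1:1 reading and the planning values, precision would be reported as 0.75 when it is 0.51 at the protocol's own prevalence, or 0.43 to 0.67 over an assumed 20% to 40%. F1 would be 0.75 against 0.61. For invasive versus noninvasive the direction reverses. Size and direction therefore depend on the task and on what balanced means, neither of which is tied down. This should be corrected, but it does not undermine the whole study, because sensitivity and specificity do not depend on the class ratio as such.

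**What to change.** Reword Methodology e) along these lines:

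- Class weighting, resampling or augmentation is applied only to the training part of each fold.
- All eligible labelled patients stay in the test folds without resampling, and folds are split by patient. The balancing method is not stated, and if it duplicates images, a copy could otherwise sit in both training and test data.

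Add to Methodology f):

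- Sensitivity and specificity are reported directly.
- Precision, F1 and accuracy are obtained by putting those estimates into the formulas above at a stated target prevalence for each task, with a range. For cancer detection this is 0.261 if the sponsor keeps that figure. Models are compared on the reweighted values.
- The report notes that reweighting does not correct for a different blend of conditions within each class.

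The cost is one or two sentences in each place and slight extra analysis, with no new data or recruitment. The sponsor must commit to a target prevalence per task, and reported precision and F1 may look less favourable.
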